### **5.9.6 Imaging**

Different imaging techniques can be used for the assessment of vascular involvement depending on the localization and types of the involved vessels.

For Deep Vein Thrombosis, Doppler ultrasound investigation and/or MRI will be used.

For the assessment of arterial aneurysms, including pulmonary artery aneurysms, CT and/or MR imaging will be performed. [REDACTED]

For Neurologic Involvement, cranial MR imaging will be preferred. MR imaging is extremely useful in differentiating NBD from its mimics. The brainstem–thalamic–basal ganglia lesions, in the proper clinical context can strongly support the diagnosis of acute/subacute parenchymal NBD. [REDACTED]

## **5.10 Safety**

### **5.10.1 Physical examination**

A complete physical examination will be performed at all study visits. It will include the examination of general appearance, skin, neck (including thyroid), eyes, ears, nose, throat, lungs, heart, abdomen, back, lymph nodes, extremities, vascular and neurological.

Information for all physical examinations must be included in the source documentation at the study site. Significant findings that are present prior to the start of study drug must be included in the Relevant Medical History/Current Medical Conditions screen on the subject's CRF. Significant findings made after the start of study drug, which meet the definition of an AE must be recorded on the AE screen of the subject's CRF.

### **5.10.2 Vital signs**

Vital signs will be assessed at Screening, at all study visits. This will include measurement of subject's body temperature, blood pressure (BP) and pulse.

Body temperature will be measured by the investigator at each visit using established methods such as tympanic measurements. In addition, subject will measure the subject's body temperature (tympanic or axillary) during occurrence of fever and record it in the subject's diary if they experience fever.

Systolic and diastolic blood pressure and radial pulse rate will be assessed after the subject has rested in the supine position for at least 3 minutes. Blood pressure should be assessed on the same arm each time measurements are taken. These data will be recorded in the CRF.

### **5.10.3 Height and weight**

Height will be measured in centimeters at Screening.

Body weight (in indoor clothing, but without shoes) will be measured to the nearest 0.1 kilogram (kg) at , Screening, Visit 5, and Visit 15. Laboratory evaluations clinics laboratory will be used for analysis of all specimens collected except for CRP and urine dipstick as outlined in the laboratory test section.

The investigator will evaluate the clinical significance of each laboratory value outside of the reference range. This decision should be based upon the nature and degree of the observed abnormality. The investigator may choose to repeat any abnormal result ONCE, in order to rule out laboratory error. "NCS" will be entered on the original laboratory sheet to the right of all laboratory values, which are outside the reference range, but are judged "not clinically

significant." The physician making these assessments should date and initial each form. Values, which are considered clinically significant and/or study drug related will be noted on the respective Central Lab Assessment CRF page with reference to the date, study day, and hour if applicable. A copy of each laboratory report must be placed in the subject's file. Clinically relevant deviations of laboratory test results occurring during or at completion of the study must be reported and discussed with Novartis. Repeated evaluations are mandatory until normalization or until the change is no longer clinically relevant. In case of doubt, Novartis must be contacted.

#### **5.10.3.1 Hematology**

Haemoglobin, hematocrit, white blood cells (WBC) count with differential, red blood cells (RBC) count and platelet count will be evaluated at Visits 1,3,4,7,8,9,10, and 11

#### **5.10.3.2 Clinical chemistry**

Albumin, alkaline phosphatase, total bilirubin, indirect and direct reacting bilirubin, calcium, chloride, cholesterol, creatinine (with derivation of creatinine clearance value), CPK,  $\gamma$ -GT, glucose, LDH, inorganic phosphorus,  $\alpha$ -amylase, potassium, total protein, SGOT, SGPT, sodium, triglycerides, urea/BUN and uric acid will be evaluated at Visits 1,3,4,7,8,9,10 and 11

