#### **5.5.13 Study completion and post-study treatment**

Information on the date the subject last took drug, the subject's completion or discontinuation of the study and the reason for discontinuation of the study will be recorded on the Study Completion CRF page.

Visit	Screening ***	1***	2	3	4	5	6	7	8	9	10	11	12	13	14	15
Day	-7 to 0	0	7	14	30	60	90	120	150	180	210	240	270	300	330	360
Blood biochemistry		X		X	X			X	X	X	X	X				
Inflammatory markers	X	X	X	X	X	X	X	X	X	X	X	X	X	X	X	X
Urine Test	X	X	X	X	X	X	X	X	X	X	X	X	X	X	X	X
PK markers		X	X		X	X	X			X		X				X
PD samples		X	X		X	X	X			X		X				X
MR-Doppler Imaging (PET-CT when necessary)		X	X	X	X	X	X			X		X				X
(*)CSF Puncture	X			X	X		X									
Neurological evaluation		X	X	X	X	X	X	X	X	X	X	X	X	X	X	X
BDCA (BD Current Activity)	X	X	X	X	X	X	X	X	X	X	X	X	X	X	X	X
Adverse Events	X	X	X	X	X	X	X	X	X	X	X	X	X	X	X	X
VAS for symptoms	X	X	X	X	X	X	X	X	X	X	X	X	X	X	X	X
Efficacy Assessment					X		X			X						X
Attack Assessment	X	X	X	X	X	X	X	X	X	X	X	X	X	X	X	X
Steroid usage assessment	X	X	X	X	X	X	X	X	X	X	X	X	X	X	X	X
Physician&Patient Global Assessment		X	X	X	X	X	X	X	X	X	X	X	X	X	X	X
Drug Administration		X			X	X	X	X	X	X	X	X	X	X	X	X

\*Optional

\*\* PPD test could be used within 6 months before patient study entry

**\*\*\* If needed, in Patient's emergency situation, Screening and Visit 1 assessment could be combining by the physician decisions. There is no need to be repeated same test for each visit (screening and visit 1)**

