## 5.7 Patient demographics/other baseline characteristics

Patient demographic and baseline characteristic data to be collected on all patients include: date of birth, age, sex, ethnicity, patient referral source, relevant medical history/current medical condition present before signing informed consent. Where possible, diagnoses will be recorded, not symptoms.

Subjects should be seen for all post-baseline visits on the designated day with the allowance of a  $\pm 7$  day window for all visits. Subjects who discontinue study drug before completing the study, and those who prematurely withdraw from the study for any reason, should be scheduled for a visit 8 weeks ( $\pm 1$  week) after their last infusion /injection, at which time all of the assessments listed for the final visit will be performed.

Subjects who discontinue study drug also should return for a last assessment. If they refuse to return for this or are unable to do so, every effort should be made to contact them or a knowledgeable informant by telephone to determine the reason for discontinuation. At a minimum, they will be contacted for safety evaluations during the 30 days following the last dose of study drug, including final contact at the 30-day point. Documentation of attempts to contact the patient should be recorded in the patient record.

Information that will be collected on subjects who are screened but not enrolled includes patient demographics (age, gender, and ethnicity) and primary reason for not continuing.

If a patient discontinues before entering Visit 1, only the demographic information and Screening Log entry with the primary reason for discontinuation should be completed on the CRF. It is not necessary to complete all the required evaluations at the time of discontinuation unless medically indicated.

At screening visit information on age, sex, will be collected. Relevant medical history/current medical conditions, family medical history, will be recorded on the respective CRF page. The following should be recorded on the respective CRF page.

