### 5.10.7 Pharmacokinetics

All blood samples will be taken by either direct venipuncture or an indwelling cannula inserted in a forearm vein. It is important to note that the volume of blood sampling will be adapted to the age of the child according to clinical practice at the investigator site. For each scheduled PK sample, 2 mL of blood will be drawn into a plain barrier tube to obtain 1 ml serum. The sample will be allowed to clot during 45 minutes at room temperature. The serum will be obtained by centrifugation at approximately 2500 g for 10 minutes. The sample will be split into two aliquots to be transferred into polypropylene screw-cap tubes. Serum tubes will be frozen within 90 min of venipuncture and kept at  $\leq -18^{\circ}\text{C}$  pending analysis. One of the two serum samples is to be kept at the study site as a backup while the other one will be shipped to the analytical center.

Time points for canakinumab PK sample collection at Visits:

- Day 0 (Visit 1)
- Day 7 (Visit 2)
- Day 30 (Visit 4); pre-dose
- Day 60 (Visit 5); pre-dose
- Day 90 (Visit 6) pre-dose
- Day 180(Visit 9) pre-dose
- Day 240(Visit 11) pre-dose
- Day 360 (Visit 15) pre-dose

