### **8.5.2 Safety variables**

The assessment of safety will be based mainly on the frequency of adverse events, which includes all serious adverse events. Adverse events will be summarized by the number and percentage of subjects having any adverse event, having an adverse event in each body system and having each individual adverse event. Any other information collected (e.g. severity or relatedness to study medication) will be listed as appropriate.

Newly occurring notable laboratory values and newly occurring vital sign abnormalities will be tabulated. Listings with abnormalities flagged will be provided

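### No scheduled haematology or chemistry panel is taken after Day 240, although dosing runs to Day 330 or Day 360 and the trial is meant to describe one year of safety

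*Combined protocol and SAP*

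**What the plan says.** Haematology (section 5.10.3.1) "will be evaluated at Visits 1,3,4,7,8,9,10, and 11". Chemistry (section 5.10.3.2) has the same list: "urea/BUN and uric acid will be evaluated at Visits 1,3,4,7,8,9,10 and 11". In the assessment schedule, the row "Blood biochemistry" is marked at exactly those visits and is blank at Visits 12 to 15. The pharmacokinetic sampling list fixes the days: "Day 240(Visit 11) pre-dose" and "Day 360 (Visit 15) pre-dose".

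Section 3.1 gives a first dose, five further monthly doses to month 5, then six more from month 6. The assessment schedule marks drug administration at Visit 1 and at every visit from 4 to 15.

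For analysis, section 8.5.2 says: "Newly occurring notable laboratory values and newly occurring vital sign abnormalities will be tabulated". It sets no time limit. Under section 5.7, patients who stop early return 8 weeks after their last dose, "at which time all of the assessments listed for the final visit will be performed".

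The title promises the safety of one year of treatment, and safety is part of the primary objective. Section 5.10.3 expects clinically relevant laboratory deviations to be reported up to and including study completion.

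**The concern.** The period over which blood counts, liver enzymes and creatinine are scheduled is shorter than the period the trial sets out to describe. After Day 240, an empty cell in the haematology and chemistry tables would mean that nothing was scheduled, but a reader would take it to mean that nothing was found.

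Early leavers have the same problem in another form. Their exit visit copies the final-visit list, which has no such panel, and those who leave because of an adverse event are the patients whose exit values matter most.

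With about 10 patients, one undetected abnormality moves a reported percentage by 10 points (1/10).

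**Working it through.** **Inputs**
- Panel visits 1, 3, 4, 7, 8, 9, 10, 11 (sections 5.10.3.1 and 5.10.3.2). By the schedule's day row these are Days 0, 14, 30, 120, 150, 180, 210 and 240.
- Final visit: Visit 15, Day 360.
- Visit window: ±7 days (section 5.7).
- Doses by the text of section 3.1: 1 + 5 + 6 = 12, at Days 0, 30, …, 150 and then 180, …, 330. Partial responders also reach 12 (1 + 1 + 4 + 6).
- Doses by the assessment schedule: Day 0 and every 30 days from Day 30 to Day 360, which is 13.

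**Does the text agree with the schedule?** For chemistry, the row in the schedule and the visit list in the text match exactly, so the stop at Day 240 is not an artefact of a broken table. No haematology row is visible in the schedule as read, so haematology rests on section 5.10.3.1 alone.

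**Time without a scheduled panel**
- Over the study period: (360 − 240)/360 = 120/360 = 33%.
- To a Day 330 last dose: (330 − 240)/330 = 90/330 = 27%.
- With the Visit 11 window: (360 − 247)/360 = 31% to (360 − 233)/360 = 35%.

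**Doses with no later scheduled panel**

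| Source | Doses from Day 240 onward | Share | Doses strictly after Day 240 | Share |
|---|---|---|---|---|
| Text | 240, 270, 300, 330 | 4/12 = 33% | 3 | 3/12 = 25% |
| Schedule | 240, 270, 300, 330, 360 | 5/13 = 38% | 4 | 4/13 = 31% |

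The Day 240 dose counts as having no later panel because the panel at that visit is not a later one.

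**Early leavers.** There is also no panel between Visit 4 (Day 30) and Visit 7 (Day 120), a gap of 120 − 30 = 90 days. Take a patient dosed at Days 30, 60 and 90 who stops before Day 120. The exit visit falls at about Day 90 + 56 = Day 146, with the final-visit assessments only. That patient has no scheduled panel after Day 30.

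**Effect of adding a panel at Visit 15, before any dose that day.** The doses at Days 240, 270, 300 and 330 then have a later panel. The count without one falls from 4 of 12 to 0 of 12 by the text, and from 5 of 13 to 1 of 13 by the schedule. The interval between panels is still 360 − 240 = 120 days.

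**The case against.** The best defence is that much else is observed to Day 360. Urine dipstick (section 5.10.3.3) and CRP, ESR and SAA (section 5.7.2) are scheduled at every visit. Adverse events, on which section 8.5.2 mainly bases safety, are sought at every visit, and a laboratory value that is clinically significant, causes symptoms or needs therapy counts as one (section 6.1). Abnormalities already found must be followed until they resolve or stop being clinically relevant. The study is small and exploratory, and panel frequency is a design choice.

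Much of this stands, and it rules out several stronger readings that a reader might infer:
- *The laboratory tables are empty after Day 240.* They are not. Urinalysis and inflammatory markers continue, and unscheduled tests may add values.
- *Later haematology or chemistry abnormalities cannot appear.* They can, if an event prompts a test. Section 8.5.2 does not restrict the table to scheduled samples.
- *A one-year laboratory rate is biased by a known amount.* Section 8.5.2 defines no such rate, only a tabulation, and the documents give no basis for quantifying a shortfall.
- *No early leaver has bloods near stopping.* Non-responders dropped at the first-month evaluation have the Visit 4 panel, and patients who stop at Visits 7 to 11 have one at that visit. The exit visit 8 weeks after the last dose is the one that lacks it.

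What the defence does not answer is the silent abnormality. Dipstick and inflammatory markers do not replace blood counts, liver enzymes or creatinine. Mandatory repeats follow only what has already been detected. Lack of power is no answer either, because a descriptive safety table depends on sampling and not on power.

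**Conclusion.** The point holds for scheduled haematology and chemistry. The plan schedules neither after Day 240 nor at the early-exit visit, while treatment goes on for a further 90 days (text) or 120 days (schedule). About a quarter to a third of the period (27% to 33%, depending on the denominator) is unsampled, and a third or more of the doses (4 of 12 or 5 of 13) have no later scheduled panel. The consequence is that new silent abnormalities in that period would not be systematically detected, so the table in section 8.5.2 can understate them. Whether it would do so in these patients, and by how much, cannot be known from the documents.

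This rests on two assumptions: that the visit list in section 5.10.3.1 is the full haematology schedule, and that visits fall near their nominal days. The conclusion is the same whether the last dose is on Day 330 or Day 360.

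**What to change.** 1. Add haematology and chemistry at Visit 15 in sections 5.10.3.1 and 5.10.3.2 and in the assessment schedule. Through section 5.7 this also puts them into the early-exit visit. Blood is already drawn at Visit 15 for inflammatory markers and PK/PD, so the cost is about one local panel per patient, or about 10 in all.
2. State in section 8.5.2 that no scheduled haematology or chemistry values exist between Day 240 and the final panel, so the onset of an abnormality in that interval cannot be dated. This costs one sentence.
3. Reconcile section 3.1 with the assessment schedule on the day of the last dose, since this decides whether any dose follows the final panel.

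One panel at Visit 15 supplies an end-of-study and exit value. It does not close the 120-day interval or the Day 30 to Day 120 gap. If the sponsor wants onset dated after Day 240, panels at Visits 12 to 15 would cut the interval to 30 days, at 4 per patient or 40 for 10 patients.

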#### **5.10.3.3 Urinalysis**

Urine sample will be obtained for semi-quantitative 'dipstick' measurements of specific gravity, pH value, protein, glucose, bilirubin, ketones, leukocytes, and blood at Screening and all subsequent visits.

In case blood and/or leukocytes, and/or protein show traces/values in the 'dipstick' evaluation, a microscopic examination including RBC, WBC, and casts will be performed by the local laboratory. If casts are noted, the type is to be specified on the relevant local lab Assessment CRF (a note should be attached to the line referring to the urinalysis collection field).

#### **5.10.4 Electrocardiogram (ECG)**

A standard 12 lead ECG will be performed at Screening and End of Study Visit.

The investigator will review the ECG, sign and date the tracing, and record any significant findings in the CRF. The CRF will contain the ventricular rate, PQ or PR interval, QRS duration, QT interval (uncorrected) and the overall interpretation (normal, clinically insignificant abnormality, clinically significant abnormalities which need to be specified further).

Each ECG tracing should be labelled with the study number, patient initials, patient number, date, and kept in the source documents at the study site.

Clinically significant abnormalities at Screening should also be recorded on the relevant medical history/Current medical conditions CRF page.

### 5.10.5 Pregnancy and assessments of fertility

Canakinumab should not be given to pregnant women. Female subjects of child-bearing potential must undergo pregnancy testing throughout the study and need to agree to an effective method of contraception during the entire study and for at least 3 months after study completion. **Serum test and/or urine test are mandatory for pregnancy at the screening visit for woman .** Other assessments

### 5.10.6 CSF Collection

CSF analyses that were performed within 3 weeks before the study entry could also be used. CSF cell count analysis will be performed in the local laboratory [REDACTED]

Each CSF sample will consist of 1 mL to be collected in a sterile polypropylene tube that contain no preservatives. After collection, the sample may be stored at 4°C. However, it must be processed to centrifugation within 1 hour of the lumbar puncture. Longer storage times at 4°C must be documented accordingly in the source documents and CRF. [REDACTED]

Sample tubes are centrifuged at 4000 x g for 10 minutes at 4°C to pellet cells and other insoluble material. The supernatant is then transferred to a new sterile polypropylene tube and gently mixed by inversion. Two (2) aliquots (0.5 mL) of the supernatant are dispensed to 0.5 mL polypropylene cryovials. This procedure limits oxidation effects by minimizing empty space in the cryovials. The 0.5 mL cryovials containing the CSF aliquots as well as the polypropylene tubes containing the cell pellets are immediately placed on dry ice.

Once completely frozen, the tubes are transferred to a freezer for storage below -70°C until shipment to the central lab. The samples must be packed on sufficient dry ice for shipment to the central lab without thawing. Upon arrival at the central lab, CSF samples must be stored below -70°C. Any thawing of frozen samples must be avoided.

Sampling problems will be noted in the CRF as an attached note.

### 5.10.7 Pharmacokinetics

All blood samples will be taken by either direct venipuncture or an indwelling cannula inserted in a forearm vein. It is important to note that the volume of blood sampling will be adapted to the age of the child according to clinical practice at the investigator site. For each scheduled PK sample, 2 mL of blood will be drawn into a plain barrier tube to obtain 1 ml serum. The sample will be allowed to clot during 45 minutes at room temperature. The serum will be obtained by centrifugation at approximately 2500 g for 10 minutes. The sample will be split into two aliquots to be transferred into polypropylene screw-cap tubes. Serum tubes will be frozen within 90 min of venipuncture and kept at  $\leq -18^{\circ}\text{C}$  pending analysis. One of the two serum samples is to be kept at the study site as a backup while the other one will be shipped to the analytical center.

Time points for canakinumab PK sample collection at Visits:

- Day 0 (Visit 1)
- Day 7 (Visit 2)
- Day 30 (Visit 4); pre-dose
- Day 60 (Visit 5); pre-dose
- Day 90 (Visit 6) pre-dose
- Day 180(Visit 9) pre-dose
- Day 240(Visit 11) pre-dose
- Day 360 (Visit 15) pre-dose

#### **5.10.7.1 Analytical method(s)**

Analytes, media and methods: canakinumab in serum by competitive ELISA, limit of quantification (LOQ) at 100 ng/mL.

Details of the analytical methods to assess canakinumab in serum will be described in the bioanalytical data report.

#### **5.10.7.2 PK sample handling, labeling and shipment instructions**

##### **5.10.7.2.1 Sample labeling**

Serum tubes will be used to collect samples.

The samples for the pharmacokinetic profile will be labeled as follows:

PK

Study Code: CACZ885NTR01

Subject Number:

Sample Number:

Date / Study Day:

Labels will be provided to the investigator with all label information preprinted on the label.

The actual sample collection date and exact time will be entered on the PK Blood Collection

Log CRF page. Sampling problems will be noted on the PK Blood Collection Log CRF

##### **5.10.7.2.2 Shipment of pharmacokinetic samples to Central Laboratory**

For each shipment, all pharmacokinetic samples are to be entered in the shipping log which can be found in the central laboratory manual. The original document will be retained at the site in the Investigator's file, and a copy of the PK Samples Shipping Log page must be included with the package of PK samples shipped.

- Day 360 (Visit 15); pre-dose

All PK/PD samples will be shipped to the following vendor:

[REDACTED]  
[REDACTED]  
[REDACTED]  
[REDACTED]  
phone [REDACTED]  
fax [REDACTED]

#### **5.10.8.2 Analytical method(s)**

Total IL-1 $\beta$  will be analyzed in serum by means of a competitive ELISA assay, limit of quantification at 1.00 pg/mL.

##### **5.10.8.2.1 Sample labeling**

Serum tubes will be used to collect samples.

The samples for the pharmacodynamic profile will be labelled as follows:

PD

Study Code: CACZ885NTR01

[figure not shown]
Subject Number:

[figure not shown]
Sample Number:

[figure not shown]
Date / Study Day:

Labels will be provided to the investigator with all label information pre-printed on the label. The actual sample collection date and exact time will be entered on the PD Blood Collection CRF page. Sampling problems will be noted on the PD Blood Collection Log CRF (a note should be attached to the line referring the PD blood collection field).

For each shipment, the same procedure described above has to be followed.

